#### 11.2.4. Feasibility End Point Analysis

Summary statistics will be presented for the overall (combined) EBQ and PBQ scores for each screening test. The overall scores will be calculated using the method described in Appendix 1. Paired t-tests will be conducted to compare the mean overall scores between pairs of screening tests (MRI & PSA, MRI & ultrasound, and ultrasound & PSA), for EBQ and PBQ scores separately. Pre-screening test scores are measured using the EBQ, and post-screening test scores are measured using the PBQ. Paired t-tests will also be used to compare the mean difference between pre- and post-screening test scores, for each screening test separately.

Each component of EBQ and PBQ is represented by a single question. EBQ has a total of four components (four questions), and PBQ has a total of five components (five questions) (see Appendix 1 for further details). Both EBQ and PBQ share four common components (embarrassment, pain, burden, anxiety).

Summary statistics will be presented for the separate components for the EBQ. These will be reported as the proportions within each value of the Likert score, for each EBQ component, measured for each screening test (PSA, ultrasound and MRI). The mean scores of each EBQ component, measured for each screening test (PSA, ultrasound and MRI) will also be calculated and reported. Paired t-tests will compare the mean EBQ component scores between pairs of screening tests (MRI & PSA, MRI & ultrasound, and ultrasound & PSA). A similar analysis will be conducted for the PBQ component scores.

Paired t-tests will compare the mean difference between pre- and post-screening test scores, for each common component of EBQ and PBQ (embarrassment, pain, burden and anxiety).

The proportions of preference for each screening test, as measured by EBQ (“Expected preference”) and PBQ (“Final preference”) separately, will be reported.

Further analysis will be conducted on screening test preference, as measured by PBQ, after the screening tests. Screening test preference will be dichotomised in four ways, as outlined in Section 10.3.9. A multivariable logistic regression model will be fit to each of these newly generated dichotomous variables, separately, controlling for pre-specified baseline patient factors. If any of the factors have more than 10% missing data then we will not include the factor in the multivariable logistic regression. The number of pre-specified baseline patient factors to be included in the

Imperial Clinical Trials Unit	STATISTICAL ANALYSIS PLAN	PROSTAGRAM
-------------------------------	---------------------------	------------

models is to be determined based on the number of cases in each of the categories of the dichotomised screening test preference variables (see Section 10.3.9) (approximately one variable per 10 cases of the smaller category). The pre-specified factors have been ranked in order of importance for inclusion in the described models. The ranked pre-specified patient factors are:

1. Age: < 60 years vs  $\geq$  60 years
2. Previous PSA: Yes vs No
3. Previous DRE: Yes vs. No
4. Ethnicity: Black vs. All other ethnicities
5. Any first degree relative (brother/father) with a history of prostate cancer: Yes vs. No
6. IMD quintile
7. Highest level of qualification: University degree vs All other responses
8. Length of relevant procedure, excluding set up time: (Phlebotomy (PSA)/US/MRI) – as measured for the screening test in the dichotomised preference variable
9. IPSS score: Mild vs. Moderate/Severe
10. Charlson Co-morbidity Index: Severe ( $\geq$ 2) vs. Not severe (< 2)
11. BMI: < 30kg/m^2 vs  $\geq$  30kgm^2
12. EBQ pain of relevant test (PSA/US/MRI): Not at all vs. All other categories – as measured by the EBQ for the screening test in the dichotomised preference variable
13. EBQ anxiety of relevant test (PSA/US/MRI): Not at all vs All other categories – as measured by the EBQ for the screening test in the dichotomised preference variable
14. EBQ embarrassment of relevant test (PSA/US/MRI): Not at all vs All other categories – as measured by the EBQ for the screening test in the dichotomised preference variable
15. EBQ burden of relevant test (PSA/US/MRI): Not at all vs All other categories – as measured by the EBQ for the screening test in the dichotomised preference variable

Odds ratios, their corresponding 95% confidence intervals, and p-values will be reported for each patient factor in each multivariable analysis.

Summary statistics will also be reported for the time taken to complete each test. Time taken will be recorded using two measurements: the length of procedure, and the length of procedure and set up.

The proportion of participants who undergo a repeat screening assessment for MRI, ultrasound and/or PSA will be reported. Summary statistics of incidental findings detected by MRI and ultrasound screening tests will also be reported.

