## 11.4. Subgroup Analysis

### 11.4.1. Subgroup Analysis End Points

Subgroup analysis will focus on the other test performance (MRI and US) end points relating to positive test rates for MRI and ultrasound, namely:

- The proportion of men with a screen-positive MRI defined by a score of 3 or greater (PIRADS only)
- The proportion of men with a screen-positive MRI defined by a score of 4 or greater (PIRADS only)
- The proportion of men with screen-positive prostate ultrasound defined by a score of 3 or greater (US)
- The proportion of men with screen-positive prostate ultrasound defined by a score of 4 or greater (US).

The subgroup analysis will be limited to the continuous age variable. The other variables required for the analysis of the end points above are described in Sections 10.3.1 and 10.3.2.

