Ethnicity (Black vs Other)	x.xxx (x.xx to x.xx)	x.xxx	x.xxx (x.xx to x.xx)	x.xxx	x.xxx (x.xx to x.xx)	x.xxx	x.xxx (x.xx to x.xx)	x.xxx
Any first degree relative with history of prostate cancer (Yes vs No)	x.xxx (x.xx to x.xx)	x.xxx	x.xxx (x.xx to x.xx)	x.xxx	x.xxx (x.xx to x.xx)	x.xxx	x.xxx (x.xx to x.xx)	x.xxx
IMD quintile (Lowest quintiles vs Higher quintiles)	x.xxx (x.xx to x.xx)	x.xxx	x.xxx (x.xx to x.xx)	x.xxx	x.xxx (x.xx to x.xx)	x.xxx	x.xxx (x.xx to x.xx)	x.xxx
Qualification level (University degree vs Other)	x.xxx (x.xx to x.xx)	x.xxx	x.xxx (x.xx to x.xx)	x.xxx	x.xxx (x.xx to x.xx)	x.xxx	x.xxx (x.xx to x.xx)	x.xxx
Length of relevant procedure	x.xxx (x.xx to x.xx)	x.xxx	x.xxx (x.xx to x.xx)	x.xxx	x.xxx (x.xx to x.xx)	x.xxx	x.xxx (x.xx to x.xx)	x.xxx
IPSS score 	x.xxx	x.xxx	x.xxx	x.xxx	x.xxx	x.xxx	x.xxx	x.xxx

Imperial Clinical Trials Unit	STATISTICAL ANALYSIS PLAN	PROSTAGRAM
-------------------------------	---------------------------	------------

(Mild vs Moderate/Severe)	(x.xx to x.xx)		(x.xx to x.xx)		(x.xx to x.xx)		(x.xx to x.xx)	
CCI  (Severe (≥ 2) vs Not Severe (< 2))	x.xxx (x.xx to x.xx)	x.xxx	x.xxx (x.xx to x.xx)	x.xxx	x.xxx (x.xx to x.xx)	x.xxx	x.xxx (x.xx to x.xx)	x.xxx
BMI (< 30kg/m  vs ≥ 30kg/m  )	x.xxx (x.xx to x.xx)	x.xxx	x.xxx (x.xx to x.xx)	x.xxx	x.xxx (x.xx to x.xx)	x.xxx	x.xxx (x.xx to x.xx)	x.xxx
Expected pain (Not at all vs Other)	x.xxx (x.xx to x.xx)	x.xxx	x.xxx (x.xx to x.xx)	x.xxx	x.xxx (x.xx to x.xx)	x.xxx	x.xxx (x.xx to x.xx)	x.xxx
Expected anxiety (Not at all vs Other)	x.xxx (x.xx to x.xx)	x.xxx	x.xxx (x.xx to x.xx)	x.xxx	x.xxx (x.xx to x.xx)	x.xxx	x.xxx (x.xx to x.xx)	x.xxx
Expected embarrassment (Not at all vs Other)	x.xxx (x.xx to x.xx)	x.xxx	x.xxx (x.xx to x.xx)	x.xxx	x.xxx (x.xx to x.xx)	x.xxx	x.xxx (x.xx to x.xx)	x.xxx
Expected burden (Not at all vs Other)	x.xxx (x.xx to x.xx)	x.xxx	x.xxx (x.xx to x.xx)	x.xxx	x.xxx (x.xx to x.xx)	x.xxx	x.xxx (x.xx to x.xx)	x.xxx

See Appendix 1 and Section 10.3.9

See Section 11.2.4

See Appendix 1

Imperial Clinical Trials Unit	STATISTICAL ANALYSIS PLAN	PROSTAGRAM
-------------------------------	---------------------------	------------

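### The no-preference model is assigned five test-specific covariates that have no value in it; age and BMI are needlessly split in two; and the IMD coding differs between places in the SAP

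*SAP*

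**What the plan says.** SAP 10.3.9 turns the post-test preference question into four yes/no outcomes: PSA, MRI, ultrasound and no preference, each against every other response. SAP 11.2.4 fits a multivariable logistic model to each, using one list of 15 baseline factors. "The pre-specified factors have been ranked in order of importance for inclusion in the described models", and the number admitted is "approximately one variable per 10 cases of the smaller category". A factor with more than 10% missing data is left out.

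Three features of the list matter here.

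- **Test-specific factors.** Rank 8, procedure length, is to be taken "as measured for the screening test in the dichotomised preference variable". Ranks 12 to 15 (expected pain, anxiety, embarrassment and burden) are tied to the outcome's test in the same way.
- **Age and BMI.** Rank 1 is entered as "Age: < 60 years vs" 60 or older, and rank 11, BMI, is split at 30 kg/m². For the models of MRI and ultrasound positivity, SAP 11.4.1 says: "The subgroup analysis will be limited to the continuous age variable".
- **IMD.** The list entry is only "6. IMD quintile". Appendix 2 (Table 2) also gives quintiles without grouping. The row label in Table 1.3.12 begins "IMD quintile (Lowest quintiles vs Higher quintiles" and carries one odds ratio per model. No cut point is given.

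**The concern.** A pre-specified model should leave no covariate definition to be chosen once the data are in hand. For the no-preference outcome, five of the 15 factors have no definition. Each man has a procedure time and a set of expected-burden answers for each of three tests (Table 1.3.13; Appendix 1, 20.1.3), and nothing says which to use or how to combine them. The IMD grouping is open in the same way.

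Splitting age and BMI raises a different issue, which is efficiency. A binary term and a linear term each cost one parameter, so the split saves nothing under the 10-per-variable rule and discards within-group information. All the resulting odds ratios, intervals and p-values are to be reported in the primary outcome paper.

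**Working it through.** **Size available.** The SAP gives no expected preference split, so the only bound is the study size. Its own formula reproduces: 1.96² × 0.611 × 0.389 / 0.05² = 365.2, rounded up to 366. Allowing for 10% dropout, 366 / 0.9 = 406.7, against the stated 406. I use 366, so the smaller category can be at most 183 men.

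**When each factor enters.** At one factor per 10 cases, a factor of rank *r* enters at about 10*r* men in the smaller category.

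| Factor | Rank | Men needed | Share of 366 |
|---|---|---|---|
| Age | 1 | 10 | 2.7% |
| IMD | 6 | 60 | 16.4% |
| Procedure length, relevant test | 8 | 80 | 21.9% |
| BMI | 11 | 110 | 30.1% |
| EBQ items, relevant test | 12–15 | 120–150 | 32.8–41.0% |

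In the no-preference model, the first undefined factor is therefore reached at about 80 men. If a higher-ranked factor is dropped for missing data and lower ranks move up, which the SAP neither states nor excludes, each such drop lowers this by about 10 (one drop: 70 men, 19.1%). Without the five undefined factors, ten remain, and a full model needs 10 × 10 = 100 men (27.3% of 366).

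**Cost of splitting age.** The share of information on a linear effect that a split keeps is the squared correlation between the variable and its two-group version. Assume age is uniform over 50–69, treated as the interval 50 to 70. The variance is 20²/12 = 33.33. The two group means lie 5 years either side of 60, so the between-group variance is 25. The share kept is 25 / 33.33 = 0.75. In whole years it is 25 / 33.25 = 0.752.

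**Cost of splitting BMI.** The documents give no BMI mean or SD, so these are assumptions. For a normal variable cut at 30, with z = (30 − mean)/SD and p the share above the cut, the share kept is φ(z)² / [p(1 − p)].

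| Mean, SD | z | Share kept |
|---|---|---|
| 26.5, 4 | 0.875 | 0.479 |
| 27, 4 | 0.750 | 0.517 |
| 28, 4.5 | 0.444 | 0.592 |

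**IMD and the parameter count.** On the two-group coding of Table 1.3.12, IMD is one parameter. Sixty men then admit 6 factors and 6 parameters, and 80 men admit 8 and 8, which is 10 per parameter in both cases. As a five-level factor IMD would take 4 parameters, 3 more than the rule counts: 60/9 = 6.7 and 80/11 = 7.3 cases per parameter.

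**The case against.** A reader might infer that the models break their own overfitting limit as soon as IMD enters. The documents do not support that. The only place that shows how IMD is modelled is Table 1.3.12, with a two-group contrast and a single odds ratio. The 6.7 and 7.3 figures need a five-level coding that is nowhere stated, and the rule is itself worded as approximate. What stands is that the list and Appendix 2 say one thing, the table another, and the cut point is missing.

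A reader might also infer that the no-preference model cannot be fitted as specified. That is too strong. With fewer than about 80 men in the smaller category, and no moving up of ranks, none of the five factors is reached and the model runs as written. The gap in definition is there at any size; its effect is conditional.

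On age and BMI, the cuts are fixed in advance and agree across 11.2.4, Table 1.3.12 and Appendix 2. The continuous-age analysis in 11.4 asks a different question, with age as the sole predictor, so there is no contradiction. The retained-information figures assume linear effects and, for BMI, a distribution that the documents do not give. BMI may never enter, since it needs about 110 men. All of this stands. It makes the split an avoidable inefficiency rather than an error.

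**Conclusion.** The point holds as a minor one, in three parts of unequal weight.

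1. Five factors are undefined in the no-preference model although the table shell expects results for them. This rests on the text alone. It affects the fit from about 80 men in the smaller category, or somewhat fewer if ranks move up.
2. Splitting age affects every model with at least about 10 men in the smaller category and gives up about a quarter of the information on a linear effect if age is roughly uniform. Splitting BMI would give up about 41–52% under the assumed distributions, but only where BMI enters.
3. The IMD coding is inconsistent and lacks a cut point. Undercounting by 3 parameters follows only if IMD is fitted with five levels.

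The models belong to a secondary acceptability analysis. The primary end point, the sample size and the test-performance results do not depend on them.

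**What to change.** - Remove ranks 8 and 12 to 15 from the no-preference model, and blank those five cells in its column of Table 1.3.12.
- Enter age and BMI as continuous terms in 11.2.4, Table 1.3.12 and Appendix 2.
- Choose one single-parameter coding for IMD, for example a linear trend across quintiles, and use it in all three places, so that one variable equals one parameter and the 10-per-variable rule means what it says.
- State whether lower ranks move up when a factor is left out.

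The cost is SAP wording and a revised table shell, with no new data. The one statistical price is that continuous terms, and a trend for IMD, assume linearity on the log-odds scale.

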#### 11.2.5. Other End Point Analysis

Biopsy related adverse events (see Section 10.3.7) will be summarised. Proportions of patients who experience each symptom, patients in whom the symptom caused a problem, and patients who had contact with healthcare will be reported.

### 11.3. Safety Analysis

At the final visit, the adverse and serious adverse events should be reconciled on the eCRF. Reported adverse events (AEs) and serious adverse events (SAEs) will be listed and summarised separately. A separate table will summarise study-related adverse events (see Appendix 3). Expected adverse events are listed in Appendix 3.

All other safety variables will be summarised by time point in the form of frequency tables for categorical variables or descriptive statistics for continuous variables.

Imperial Clinical Trials Unit	STATISTICAL ANALYSIS PLAN	PROSTAGRAM
-------------------------------	---------------------------	------------

## 11.4. Subgroup Analysis

### 11.4.1. Subgroup Analysis End Points

Subgroup analysis will focus on the other test performance (MRI and US) end points relating to positive test rates for MRI and ultrasound, namely:

- The proportion of men with a screen-positive MRI defined by a score of 3 or greater (PIRADS only)
- The proportion of men with a screen-positive MRI defined by a score of 4 or greater (PIRADS only)
- The proportion of men with screen-positive prostate ultrasound defined by a score of 3 or greater (US)
- The proportion of men with screen-positive prostate ultrasound defined by a score of 4 or greater (US).

The subgroup analysis will be limited to the continuous age variable. The other variables required for the analysis of the end points above are described in Sections 10.3.1 and 10.3.2.

### 11.4.2. Subgroup Analysis Methodology

The analysis with respect to screen-positive MRI will use the PIRADS cut-offs (see Section 10.3.1). The primary subgroup analysis of this end point is concerned with whether age is significantly associated with the probability of attaining a screen-positive MRI result. The distribution of the age variable will be evaluated. From this we will consider whether it is necessary to centre the age variable on the median for improved interpretation of the model. The screening results will be dichotomised into screen-positive and negative results using the PIRADS cut-offs defined in Section 10.3.1. A logistic regression model will be fitted to screening results on the continuous age variable. This analysis will be repeated for each of the PIRADS cut-offs (Section 10.3.1). Odds ratios and their corresponding 95% confidence intervals will be presented. The distribution of age over screen-positive and negative results (using both cut-offs defined in Section 10.3.1) will be displayed using boxplots. A similar analysis will be carried out for screen-positive ultrasound, using the US cut-offs defined in Section 10.3.2.

A secondary subgroup analysis of MRI screening results is concerned with whether age is significantly associated with PIRADS score. The distribution of the age variable will be evaluated. From this we will consider whether it is necessary to centre the age variable on the median for improved interpretation of the model. This will be evaluated by fitting an ordinal logistic model for PIRADS score on the continuous age variable. The proportional odds assumption will be tested and verified. Cumulative odds ratios and the corresponding 95% confidence intervals will be presented. The distribution of age across PIRADS scores will be displayed using boxplots. A similar analysis will be carried out to evaluate whether age is significantly associated with US score.

## 11.5. Interobserver Agreement for MRI

The reproducibility of MRI will be an important aspect of future use of MRI in the diagnostic pathway for prostate cancer. It is felt that interobserver agreement is more important than intraobserver agreement as in general practice, scans will be assessed once by a locally based radiologist.

Given that it takes approximately 30-60 minutes for a radiologist to assess a scan and complete the CRF, the workload on the central reporter will be unfeasible if all the scans are to be double reported. Thus, the interobserver agreement will be assessed on a random sample of 20% of the total MRI scans. The random sample will be stratified by PIRADS score: negative (a score of 1 or 2), intermediate (a score of 3), or positive (a score of 4 or 5). The central reader for Prostagram is [name], the Clinical Lead in MRI and Head of Imaging Research at Paul Strickland Scanner Centre, Mount Vernon Cancer Centre, London.

Imperial Clinical Trials Unit	STATISTICAL ANALYSIS PLAN	PROSTAGRAM
----------------------------------	---------------------------	------------

A 5x5 contingency table will present the agreement in PIRADS scores (see Section 10.3.1) for MRI scans between the local reader and the central reader, [name]. The Cohen's kappa statistic and corresponding 95% confidence interval will be reported to assess the level of agreement.

The kappa statistic ranges from -1 to 1. Unity represents perfect agreement between the two reviewers. A score of zero indicates agreement is no better than that expected by chance. A negative kappa indicates agreement is worse than that expected by chance.

## 11.6. Tables to Present

### 11.6.1. Baseline Characteristics

**Table 1.1. 1: Baseline Characteristics**

Demographic	Variable	Statistics	Total
Age	Age (years)	50-54 – n (%)	xxx (xx%)
		55 – 59 – n (%)	xxx (xx%)
		60-64 – n (%)	xxx (xx%)
		65 – 69 – n (%)	xxx (xx%)
		N	xxx
		Mean (SD)	xx.xx (xx.xx)
		Median (IQR)	xx.xx (xx.xx, xx.xx)
	Missing from eCRF – n (%)	xx (xx%)	
IMD	IMD Quintiles (n (%))	Quintile 1 (1 – 6496)	xxx (xx%)
		Quintile 2 (6497 – 12993)	xxx (xx%)
		Quintile 3 (12994 – 19489)	xxx (xx%)
		Quintile 4 (19490 – 25986)	xxx (xx%)
		Quintile 5 (25987 – 32482)	xxx (xx%)
		Missing from eCRF	xxx (xx%)
BMI	BMI (Kg/m  )	N	xxx
		Mean (SD)	xx.xx (xx.xx)
		Median (IQR)	xx.xx (xx.xx, xx.xx)
		Missing from eCRF – n (%)	xx (xx%)
Ethnicity	Ethnicity (n (%))	White	xxx (xx%)
		Asian	xxx (xx%)
		Black	xxx (xx%)
		Mixed Race	xxx (xx%)
		Other	xxx (xx%)
		Missing from eCRF	xxx (xx%)
Qualification level	Highest qualification level (n (%))	No formal qualifications	xxx (xx%)
		GCSEs/O-Levels/CSEs/Other	xxx (xx%)
		A-levels/Higher education below degree	xxx (xx%)
		University degree	xxx (xx%)
		Missing from eCRF	xxx (xx%)
Marital status	Marital status (n (%))	Married/Civil partnership/Co-habiting	xxx (xx%)
		Single/Divorced/Widowed	xxx (xx%)
		Missing from eCRF	xxx (xx%)
Employment status	Employment status (n (%))	Employed	xxx (xx%)
		Unemployed	xxx (xx%)

Imperial Clinical Trials Unit	STATISTICAL ANALYSIS PLAN	PROSTAGRAM
-------------------------------	---------------------------	------------

		Retired Unable to work Other (Student/Homemaker) Missing from eCRF	xxx (xx%) xxx (xx%) xxx (xx%) xxx (xx%)
Visit to GP	Visits to GP in last 12 months (n (%))	0 ≥ 1 Missing from eCRF	xxx (xx%) xxx (xx%) xxx (xx%)
Smoking status	Smoking status (n (%))	Current smoker Former smoker Never smoked Missing from eCRF	xxx (xx%) xxx (xx%) xxx (xx%) xxx (xx%)
Smoking history	Age started smoking	N Mean (SD) Median (IQR) Missing from eCRF – n (%)	xxx xx.xx (xx.xx) xx.xx (xx.xx, xx.xx) xx (xx%)
	Age stopped smoking 	N Mean (SD) Median (IQR) Missing from eCRF – n (%)	xxx xx.xx (xx.xx) xx.xx (xx.xx, xx.xx) xx (xx%)
	Pack years 	N Mean (SD) Median (IQR) Missing from eCRF – n (%)	xxx xx.xx (xx.xx) xx.xx (xx.xx, xx.xx) xx (xx%)
Heard about prostate check	How they heard about the prostate health check (n (%))	Letter from GP GP Recruitment Traditional Recruitment Social Media Recruitment Targeted Traditional Recruitment Targeted Social Media Recruitment Missing from eCRF	xxx (xx%) xxx (xx%) xxx (xx%) xxx (xx%) xxx (xx%) xxx (xx%) xxx (xx%)
Prostate history	Previous PSA test (n (%))	No (and < 2 years ago)  Yes (and > 2 years ago) 2-3 years ago 3-5 years ago > 5 years ago Unknown  Missing from eCRF	xxx (xx%)  xxx (xx%) xxx (xx%) xxx (xx%) xxx (xx%) xxx (xx%)  xxx (xx%)

Imperial Clinical Trials Unit	STATISTICAL ANALYSIS PLAN	PROSTAGRAM
-------------------------------	---------------------------	------------

	Previous DRE (n (%))	Yes No Missing from eCRF	xxx (xx%) xxx (xx%) xxx (xx%)
Family history	Family history of prostate cancer (n (%))	Any family history of prostate cancer  Any first degree relative (brother/father)   3 or more affected relatives OR at least two relatives who have developed early-onset PCa (<55 years)   Missing from eCRF	xxx (xx%)  xxx (xx%)  xxx (xx%)  xxx (xx%)
Medical history	Is the patient taking 5-alpha reductase inhibitors? (n (%))	Yes No Missing from eCRF	xxx (xx%) xxx (xx%) xxx (xx%)
	Is the patient taking an alpha blocker? (n (%))	Yes No Missing from eCRF	xxx (xx%) xxx (xx%) xxx (xx%)
Physical examination	Digital rectal examination result (n (%))	No nodule Nodule Evidence of locally advanced disease Missing from eCRF	xxx (xx%) xxx (xx%) xxx (xx%) xxx (xx%)

Former smokers only

Calculated by multiplying the number of packs of cigarettes smoked per day by the number of years the person has smoked (former smokers only)

See reference (8) for details

See reference (9) for details

